10.2 Secondary study parameter(s)

Response over time

To assess the response over time, data of mean P-SCCAI score within each arm at T = 0, 4, 8, 12 and 60 weeks will be obtained. Comparisons will be made between groups (as done for T = 8 for the primary study parameter) as well as within subjects over time. With P-SCCAI score ≤ 2 being regarded as clinical remission, and a decrease in the P-SCCAI score by more than two points from baseline being regarded as clinical response, we will determine whether subjects have reached clinical remission and/or showed a clinical response over time.

To assess the response within each subject (clinical remission and/or clinical response) over time, data of sum P-SCCAI score within each subject at T = 0, 4, 8, 12 and 60 weeks will be obtained. For comparative analyses between baseline and intervention, the parametric paired sample T-test or the non-parametrical Kruskal-Wallis or Mann-Whitney

U test will be used, depending on the distribution of the samples. Differences between treatments before and after supplement intake will also be analysed by linear mixed models for repeated measures, using “treatment” [prebiotics/placebo], “responding” [responders/non-responders], “time point” [0, 4, 8, 12 and 60 weeks] and “treatment x responding x time point” as fixed effects and subject as random effect. Clinically relevant variables such as BMI, age, sex, and medication use will be taken into account.

Mucosal inflammation

Fecal calprotectin data will be analysed in the same manner as described above (Response over time).

GI complaints:

Data from GSRS will be computed into scores, and the score of each item will be pooled together as the sum score, and the score of each item within each domain will be pooled as well. All data will be analysed in the same manner as described above (Response over time). Differences over time within and between groups will be tested with mixed model analysis. Variables such as timepoint, group, age, sex will be taken into account.

Stool consistency and frequency

Average bowel movement per day and dynamic change on stool consistency will be calculated and collected. All data will be analysed in the same manner as described above (Response over time)..

Gut microbiota and SCFAs

Fecal SCFAs data will be analysed in the same manner as described above (Response over time)

16S rRNA gene sequencing provides sequence read counts data. It will be normalized to microbial relative abundance, and microbiota diversity indices (Shannon, Simpson, and inverse Simpson) are calculated at amplicon sequence variant (ASV) level, as implemented in the Picante [66] and Phyloseq [67] packages in R, respectively. Wilcoxon test will be applied to determine whether diversity as well as the relative abundance of specific bacterial taxa, were significantly different between groups since the data was non-parametric. For microbiota analysis, *p*-values will be corrected for multiple comparisons using the Benjamini–Hochberg procedure. To correct for a false discovery rate (FDR), a FDR adjusted *p*-values will be computed, a so-called *q*-value [68]. A corrected *q*-value of less than 0.2 was considered significant. Paired tests will be used to

compare the effects of prebiotics. Pairwise weighted UniFrac [69] and unweighted UniFrac [70] distance-based principle coordinate analysis (PCoA) will be used to visualize microbial community variation at the ASV level. Permutational multivariate analysis of variance (PERMANOVA) will be used to test for significant differences between groups, as implemented in the Vegan package [71].

Health-related quality of life

Data from SIBDQ will be computed into scores, and the score of each item will be pooled together as the sum score, and the score of each item within each domain will be pooled as well. All data will be analysed in the same manner as described above (Response over time).

Medication use

Type, Dose, frequency and duration of each medication use will be collected. All data will be analysed in the same manner as described above (Response over time).

Safety parameters

Incidence rate of each adverse event is recorded and calculated. All data will be analysed in the same manner as described above (Response over time).

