2. OBJECTIVES

Primary Objective:

The primary objective is to validate the prediction that prebiotics intervention boosts butyrate production and thereby induces a higher response (lower mean Patient Simple Clinical Colitis Activity Index (P-SCCAI) score) in mild UC patients with low intestinal Bacteroidetes levels (predicted responders), but not in those with high intestinal Bacteroidetes levels (predicted non-responders) at T = 8 weeks

Secondary Objective(s):

1. To study the effects of the prebiotic intervention on response over time at T = 0, 4, 8, 12, and 60 weeks in mild UC patients
2. To study the effects of the prebiotic intervention on mucosal inflammation (fecal calprotectin levels) in mild UC patients
3. To study the effects of the prebiotic intervention on gastro-intestinal (GI) complaints (e.g., indigestion, abdominal pain) in mild UC patients
4. To study the effects of the prebiotic intervention on stool consistency and frequency in mild UC patients
5. To study the effects of the prebiotic intervention on the gut microbiota composition and SCFAs profile in mild UC patients
6. To study the effects of the prebiotic intervention on health-related quality of life in mild UC patients
7. To study the effects of the prebiotic intervention on medication use in mild UC patients
8. To study the effects of the prebiotic intervention on safety parameters in mild UC patients

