10.1 Primary study parameter(s)

Response (mean P-SCCAI score) between arms at T = 8 weeks

To assess the response, data of mean P-SCCAI score within each arm at T = 8 weeks (after the intervention) will be obtained.

Firstly, the mean P-SCCAI score between the predicted responders with prebiotics and predicted non-responders with prebiotics will be compared by using a Student T-test if normally distributed, otherwise a Mann-Whitney U test when skewed.

Secondly, the mean P-SCCAI score between prebiotics and placebo groups within predicted responders or predicted non-responders will be compared by using a Student T-test if normally distributed, otherwise a Mann-Whitney U test when skewed.

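### Section 10.2 takes its between-group tests from the stratum-specific primary comparisons, its mixed model lists no treatment-by-time term, and adverse events go through methods that do not suit counts of subjects with an event

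*Protocol*

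**What the plan says.** Section 2 words all eight secondary objectives for the same population, with no split by Bacteroidetes level. The last reads "To study the effects of the prebiotic intervention on safety parameters in mild UC patients".

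Section 10.2 (Response over time) sets the between-group tests by reference: "Comparisons will be made between groups (as done for T = 8 for the primary study parameter) as well as within subjects over time". Section 10.1 names these comparisons:

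- "Firstly, the mean P-SCCAI score between the predicted responders with prebiotics and predicted non-responders with prebiotics will be compared" (arm 1 v arm 3);
- "Secondly, the mean P-SCCAI score between prebiotics and placebo groups within predicted responders or predicted non-responders will be compared" (arm 1 v arm 2 and arm 3 v arm 4).

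Each uses a t-test or a Mann-Whitney test.

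Section 10.2 then adds a model: "Differences between treatments before and after supplement intake will also be analysed by linear mixed models for repeated measures". It is specified "using “treatment” [prebiotics/placebo], “responding” [responders/non-responders", followed by time point (0, 4, 8, 12 and 60 weeks) and one three-way product as fixed effects, with subject as random effect. No two-way term is listed.

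Calprotectin, GSRS, stool, SCFA, SIBDQ and medication data are all referred back to this paragraph, and GSRS has a further mixed model with time point and group. For safety the text is "Incidence rate of each adverse event is recorded and calculated. All data will be analysed in the same manner as described above (Response over time". The microbiota tests are described separately.

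**The concern.** Arm 1 v arm 3 compares two groups that both take the prebiotic, so it cannot show an effect of the prebiotic. The other two comparisons each use half the subjects. An effect common to both strata could be missed in both halves, or reach significance in one by chance and be reported as stratum-specific.

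The mixed model uses everyone, but without treatment by time its treatment term is not the effect during supplementation. It takes in a visit before treatment and, for some outcomes, visits after the supplement has stopped.

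The stakes are highest for tolerance and safety. The Summary and section 6.4 expect bloating or minor GI symptoms in users generally, not by Bacteroidetes level. Underpowered comparisons could then be read as good tolerance.

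**Working it through.** **Inputs from the protocol.** Two-sided alpha 0.05; 11 per arm before drop-out and 15 enrolled per arm (section 4.4); 30 subjects per stratum (section 3). P-SCCAI is collected at weeks 0, 4, 8, 12 and 60; GSRS, SIBDQ, stool and safety data at weeks 0, 4 and 8 (section 8.1.2).

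**Assumptions.** The protocol gives no effect sizes, event rates or within-subject correlations for the secondary outcomes. I take a common effect d = 0.8 SD (0.5 SD as a second case), correlation r from 0.3 to 0.7, and the event rates shown below.

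**1. The plan's own figure.** n = 2 × [0.5 × (1.960 + 1.282) / 0.7]² = 10.7, so 11 per group, as stated. A pooled contrast therefore has 2 × 11 = 22 v 22 completers.

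**2. Within-stratum v pooled test at week 8.** Noncentral t with noncentrality d / √(2/n); df 20 for 11 v 11, and df 41 for 22 v 22 adjusted for stratum.

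| Common effect | 11 v 11 | 22 v 22 |
|---|---|---|
| 0.5 SD | 20% | 37% |
| 0.8 SD | 43% | 74% |

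At 0.8 SD the two stratum tests disagree with probability 2 × 0.431 × 0.569 = 0.49. With no drop-out, 0.8 SD gives 56% (15 v 15) and 86% (30 v 30).

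**3. The treatment term as listed.** Read it as an equal-weight average over V visits and both strata, with the effect present at weeks 4 and 8 only. The signal is (2/V)d, the variance of a subject's mean is (1 + (V − 1)r)/V, and the standardised effect is their ratio on the SD scale, again at 22 v 22.

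| Outcome | V | Signal | r | Variance | Standardised effect | Power |
|---|---|---|---|---|---|---|
| P-SCCAI | 5 | 0.4 × 0.8 = 0.32 | 0.3 | 0.44 | 0.48 | 35% |
| | | | 0.5 | 0.60 | 0.41 | 27% |
| | | | 0.7 | 0.76 | 0.37 | 22% |
| GSRS, SIBDQ | 3 | 0.67 × 0.8 = 0.53 | 0.3 | 0.53 | 0.73 | 66% |
| | | | 0.5 | 0.67 | 0.65 | 56% |
| | | | 0.7 | 0.80 | 0.60 | 49% |

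The comparator is 74% for the pooled week-8 contrast.

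**4. What the model can estimate.** Two arms × two strata × five visits make 20 cells. If the three-way term is expanded to all 20, a stratum-averaged treatment contrast for the change from week 0 to week 8 is estimable. If it is entered as simple products beside the main effects, the model has rank 11, contains no treatment-by-time term, and carries that contrast only through the three-way coefficient.

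**5. Adverse events.** Exact power of Fisher's test with all subjects observed.

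| Assumed rates | 15 v 15 | 30 v 30 |
|---|---|---|
| 20% v 50% | 25% | 60% |
| 10% v 40% | 33% | 71% |

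**6. The price of pooling.** Suppose the section 4.4 difference (0.7/0.5 = 1.4 SD) is a prebiotic effect in predicted responders only. The pooled effect is then 0.7 SD. Power is 88% within the stratum (11 v 11) and 62% pooled (22 v 22).

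**The case against.** A reader might infer that no planned analysis compares prebiotics with placebo over both strata. The documents do not support that. The mixed model includes all subjects, has treatment as a fixed effect beside predicted response, and is inherited by most secondary outcomes. Its stated purpose, differences before and after intake, points to a change contrast, which is estimable under the fuller reading of the three-way term. What stands is narrower: the listed terms do not provide for that contrast, and the treatment term that is listed measures something else.

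A reader might also apply the five-visit dilution to every outcome. It does not apply to GSRS, stool, SIBDQ or safety data, which stop at week 8.

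Nor does it follow that a pooled contrast should lead every objective. The trial is built on differential response, and step 6 shows what pooling would cost there. Objective 1 also covers all the visits, so weeks 4, 12 and 60 cannot be set aside.

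The choice of a lead contrast for each secondary outcome could properly be left to a statistical analysis plan. A protocol that itself lists an incomplete set of fixed effects, and itself sends event incidence through t-tests and a linear model, is a different matter. Finally, 11 completers per arm may be pessimistic at week 8, because the 30% drop-out allowance partly reflects the one-year follow-up. The no-drop-out figures in step 2 narrow the gap but do not close it.

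**Conclusion.** The point holds in limited form. The named between-group tests do not match the wording of objectives 1-8. The one analysis over both strata is specified so that its treatment term includes the pre-treatment visit and, where measured, the visits after supplementation. For an assumed common effect of 0.8 SD, that leaves 22-35% power for P-SCCAI and 49-66% for GSRS and SIBDQ, against 74% for a pooled week-8 contrast. These figures depend on the assumed effect, its restriction to weeks 4 and 8, the correlation range, and the averaging reading of the treatment term.

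The case is strongest for safety. Half-size t or Mann-Whitney tests and a linear mixed model do not suit counts of subjects with an event, and GI symptoms are expected in users generally. The change should be made, but the primary comparisons in section 10.1 need not move.

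**What to change.** 1. **Section 10.2, Response over time.** Add the two-way terms, including treatment by time point, to the listed fixed effects. Report the stratum-adjusted prebiotics v placebo contrast at each on-treatment visit, week 8 in particular, in place of the treatment main effect.
2. **Section 10.2, Safety parameters.** Replace the reference back to Response over time with a comparison of the number of subjects with an event during the 8 weeks: prebiotics v placebo over both strata, stratified by predicted response (Mantel-Haenszel or exact).
3. **Section 10.2, GI complaints.** Use the pooled contrast from item 1 for tolerance on the GSRS.
4. **Leave in place.** Keep the stratum-specific contrasts for the efficacy outcomes and all visits for objective 1. Do not make the pooled contrast the lead for P-SCCAI.

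The cost is wording in section 10.2, with no new patients or data. The pooled estimate must be described as an average over the two enrolled strata. It weights them 30:30, although section 4.4 puts about 50% and 17% of local UC patients in them, and it leaves out patients between 10% and 15% Bacteroidetes. It is also diluted if only predicted responders benefit, which is why the stratum contrasts stay.

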4.2 Inclusion criteria

1. Male and female subjects aged 18 to 65 years*
2. Body Mass Index (BMI) between 18 and 30 kg/m² (self-reported)
3. Ulcerative Colitis confirmed via previous endoscopy and histology
4. Mild active UC as defined by P-SCCAI score of 3 to 5 (range 0 to 19)
5. Frequent relapse (at least one exacerbation in the last two years)
6. No known allergy to any components of the study product (self-reported)
7. Signed informed consent
8. Stable UC medication defined as no switch to other medication or no dose change
9. Mobile phone on which apps (used for questionnaires) can be downloaded (iOS version 9 and newer, Android version 4.4 and newer. Phones manufactured after 2013 are usually suitable)
10. Stable dietary pattern during the study

* We only include adults (age 18-65) as previous studies have shown that adolescent and elderly microbiota as well as UC presentation in adolescents can be different from adults[32, 33].

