10. STATISTICAL ANALYSIS

Statistical analyses will be done using the statistical program embedded within R. The threshold for significance will be set at $p<0.05$, with a FDR correction for 16S rRNA gene sequence data. In general, the continuous data will be presented as mean \pm standard deviation or mean and interquartile range when skewed, and categorical data as counts and percentages. Normality will be checked by visual inspection and QQ plots, followed by the Shapiro Wilk test for testing if data show a normal distribution.

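### Section 10.2, secondary analyses: the non-parametric fallback for the within-subject baseline-versus-intervention comparison is an unpaired test (minor)

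*Protocol*

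**What the plan says.** Protocol section 10.2, under Response over time, plans two kinds of comparison. Those between groups follow the week-8 primary analysis (Student t-test or Mann-Whitney U, section 10.1). The others are made "as well as within subjects over time". A separate paragraph on response within each subject then names the tests: "For comparative analyses between baseline and intervention, the parametric paired sample T-test or the non-parametrical Kruskal-Wallis or Mann-Whitney" U test, the choice "depending on the distribution of the samples". Section 10 says how distribution is judged: by visual inspection and QQ plots, "followed by the Shapiro Wilk test for testing if data show a normal distribution".

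Other outcomes take over the rule by reference, for example "Fecal calprotectin data will be analysed in the same manner as described above (Response over time". SCFAs, stool consistency and frequency, and SIBDQ are handled likewise. GSRS is too, but its paragraph also names a mixed-model analysis of differences within and between groups.

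One other sentence concerns pairing, "Paired tests will be used to" compare prebiotic effects. It stands in the 16S rRNA paragraph.

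Section 10.2 also plans a linear mixed model with subject as random effect, and with treatment, responding, time point and "treatment x responding x time point" as fixed effects.

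**The concern.** Between-group tests are assigned elsewhere, so the sentence at issue can only concern repeated measurements on the same patients, and its parametric option is accordingly a paired test. Non-normality is a reason to move to ranks, but it does not make a patient's visits independent. Mann-Whitney U and Kruskal-Wallis both assume independent samples. When visits correlate positively, they use too large a variance for the change and can miss a real within-arm change.

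The outcomes most exposed are those that may be skewed and are not restricted at entry, such as calprotectin and SCFAs. Because the protocol names the tests, this is a choice it has made and not a detail left open for an SAP.

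**Working it through.** **Inputs.** From section 4.4: 11 per group before drop-out, 15 after allowance for it, a difference of 0.7 points (3.5 v 2.8), SD 0.5, two-sided 5%, power 90%. The protocol gives no within-subject correlation, so ρ = 0.3, 0.5 and 0.7 are assumed.

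**The plan's own figure.** n = 2(1.960 + 1.282)² × 0.5² / 0.7² = 2 × 10.51 × 0.25 / 0.49 = 10.7, hence 11 per group (power 0.907 by normal approximation). It reproduces and supplies n for what follows.

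**Direction of the error.** For means, the variance of a within-subject change is 2σ²(1 − ρ)/n, whereas an independent-samples analysis uses 2σ²/n. Its standard error is too large by 1/√(1 − ρ): 1.20, 1.41 and 1.83 at ρ = 0.3, 0.5 and 0.7. Rank tests behave similarly, so the error is conservative.

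**Type I error, by simulation (correlated normal pairs, n = 11).**

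| Test | ρ = 0 | 0.3 | 0.5 | 0.7 |
|---|---|---|---|---|
| Mann-Whitney U, two visits | 5% | 2% | 1% | 0.2% |
| Kruskal-Wallis, 3 to 5 visits | 4-5% | 1.2-1.8% | 0.3-0.6% | 0.1% or less |

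Signed-rank and Friedman stay at about 4-5%.

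**Power under the protocol's own rule.** The relevant procedure is not Mann-Whitney every time. It is a paired t-test unless normality is rejected, and Mann-Whitney U otherwise. The rule was simulated with Shapiro-Wilk at 5%, applied to the two visits' samples or to the differences, with n = 11 and a shift of 0.7 SD. The lognormal case has SD of logs 1, the shift on the log scale, and signed-rank on raw differences.

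| Data | How often the fallback is taken | Rule, ρ = 0.3 / 0.5 / 0.7 | Signed-rank |
|---|---|---|---|
| Normal | 5-10% | 41 / 52 / 72% | 37 / 50 / 72% |
| Lognormal | 86-89% (samples) or 47-54% (differences) | 31 / 31-34 / 34-40% | 33 / 45 / 66% |

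Repeat runs differ by a few points. One put the rule at 31-37% and signed-rank at 63% for lognormal data at ρ = 0.7. The pattern is unchanged: no loss with normal data; with lognormal data about 2 points at ρ = 0.3, 11-14 at 0.5, and 26 or more at 0.7.

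**P-SCCAI.** Entry requires "Mild active UC as defined by P-SCCAI score of 3 to 5 (range 0 to 19"). Restricting the range lowers the correlation with later scores. For an assumed population SD of 1.5 to 2, correlations of 0.3, 0.5 and 0.7 become 0.12-0.15, 0.21-0.26 and 0.35-0.41. A fall of 0.7 points is then detected in 17-28% by Mann-Whitney and 15-33% by signed-rank, never more than 6 points apart.

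**At the planned effect size.** 0.7/0.5 = 1.4 SD. Even if Mann-Whitney were used every time on normal data, power is 89, 92 and 95% against 92, 98 and 100% for signed-rank at ρ = 0.3, 0.5 and 0.7, so at most 6 points are lost.

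**The case against.** The strongest reply is that the slip has little consequence. The analysis is secondary and within arm, the error cannot create false positives, and a mixed model that respects the repeated measures is planned beside it. All of that stands, and it keeps the point minor. It does not make an unpaired test suitable for paired data.

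Three stronger readings are tempting, and the documents do not support them.

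- A reader might infer large power losses throughout by applying Mann-Whitney to normal data every time (28 v 51% at ρ = 0.5, 26 v 73% at 0.7, for a 0.7 SD shift at n = 11). The protocol would use the paired t-test there in some 90-95% of cases.
- A reader might infer that the fallback is near certain, because Shapiro-Wilk almost always rejects whole-point scores confined to 3-5. That concerns P-SCCAI judged on baseline scores alone. Judged on differences, rejection is 12-35%. P-SCCAI is also the outcome for which the loss is small.
- A reader might infer that the mixed model is misspecified because no two-way interactions are listed. The multiplication sign may be shorthand for the full factorial. If R instead expands the listed term with time as a factor, the fitted means and the contrasts taken from them equal those of the full factorial. Trouble would require an overall test of that term, which the protocol nowhere states.

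**Conclusion.** The point holds as a minor error in section 10.2. For one within-subject comparison, the parametric test is paired and the named non-parametric alternative is not. The sentence on paired tests in the microbiota paragraph does not correct it for P-SCCAI, calprotectin, SCFAs, SIBDQ or stool data. GSRS inherits the rule too, but has its explicit mixed-model analysis.

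Confidence is high on the wording. The size rests on assumed correlations and on the lognormal as a stand-in for a skewed outcome. On those assumptions the cost is a loss of power for moderate changes in skewed outcomes when visits correlate at about 0.5 or more. It is negligible at 0.3 and absent for normal data. The primary week-8 tests and the mixed model are untouched.

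**What to change.** In the baseline-versus-intervention sentence of section 10.2, replace the Kruskal-Wallis and Mann-Whitney U tests with the Wilcoxon signed-rank test for baseline against each later visit. Use the Friedman test only if an overall test across visits is wanted, and note that it needs complete visits, which matters with the 30% drop-out expected in section 4.4. State that normality for this comparison is judged on the within-subject differences. Keep Mann-Whitney U for comparisons between arms. Outcomes that refer back to this paragraph are then corrected automatically.

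Optionally, if the listed three-way term is meant as the full factorial, write it so.

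The cost is one or two sentences. No patients, visits or data are added, and the sample size does not change.

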4.4 Sample size calculation

The primary objective of the trial is to validate the prediction that a higher response (lower mean P-SCCAI score) is induced at T= 8 weeks by the prebiotics intervention in mild UC patients with low Bacteroidetes levels (predicted responders), but not in those with high Bacteroidetes levels (predicted non-responders) in their gut. Mild UC is defined as a P-SCCAI score of 3 to 5. According to an extensive study regarding UC disease activity conducted in the Netherlands, mild UC patients have a P-SCCAI score of 3.5 ± 0.5 (Mean \pm standard deviation (SD)), and patients in remission score at 1.0 ± 0.33 (Mean \pm SD)[34, 35].

In a series of germinated barley foodstuff (GBF) intervention studies, 10 mild to moderately active UC patients received 30 grams of GBF (equals to 10 grams fiber) daily for 4 weeks [4], and researchers found a significant decrease in clinical activity index scores. In a later study, another group of 11 mildly to moderately active UC patients consuming 20-30 grams of GBF (equals to 6.66-10 g fiber) daily for 4 weeks showed similar results, with decreases in clinical activity index scores [28].

Based on two-sided statistical testing for unpaired continuous data, an $\alpha=0.05$ (chance on type-I error) and $\beta=0.10$ (chance on type-II error), and assuming a 20% difference of mean P-SCCAI score between predicted responders with prebiotics and predicted non-responders with prebiotics, it was calculated that at least 11 subjects per group are needed for the primary outcome P-SCCAI ($\mu_1=3.5$; $SD_1=0.5$; $\mu_2=2.8$). According to previous trials on prebiotics on IBD patients, a 20% of drop-out rate is commonly seen. Given that the intervention duration is 8 weeks long, followed by a 1 year follow-up, higher dropout rate (30%) is expected. To compensate for a 30% drop-out rate, 15 subjects per group are needed.

To reach inclusion of 30 predicted responders and 30 predicted non-responders, we made an estimate how many subjects we need to screen based on the earlier obtained microbial composition of stool samples from UC patients in the Ede area. Around 50% of these subjects were categorized as low Bacteroidetes subjects (predicted responders) and while 17% of them as high Bacteroidetes subjects (predicted non-responders). To include these responders we will need to screen 177 mild UC patients.

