8.2 Randomisation, blinding and treatment allocation

During the screening period, participants will provide a fecal sample for microbiome signature measurement. This information will be used to assign subjects to four intervention arms by block randomization. All subjects screened for the trial will be assigned a unique participant ID number. Suitable participants will subsequently be randomised to prebiotics or placebo group using an online randomisation system accessible via password-protected access.

All sachets will be uniformly packaged to ensure double-blinding. Research teams and trial participants will be blinded to the treatment group for the duration of the trial. After collection of all laboratory & questionnaire data and performing all analysis of the baseline/intervention period the study (up to the 4-week follow-up; T=12 weeks) will be unblinded for the investigators. At the end of the study (T=60 weeks), the participants will be informed of the kind of intervention they received. (only when approved in the informed consent).

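### The secondary mixed model in section 10.2 lets prebiotics and placebo differ at week 0 despite randomisation, so the treatment effect stays unbiased but loses precision

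*Protocol*

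**What the plan says.** Protocol section 10.2 (Response over time) states that "Differences between treatments before and after supplement intake will also be analysed by linear mixed models for repeated measures". The fixed effects are treatment, predicted-responder status, time point and the product of all three; subject is the random effect. The time point factor has the levels "0, 4, 8, 12 and 60 weeks", so week 0 is one of the outcome visits. BMI, age, sex and medication use are given as examples of covariates. The list is open, but the baseline score is not named, and no constraint on the week-0 means is stated.

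Section 8.2 says: "Suitable participants will subsequently be randomised to prebiotics or placebo group using an online randomisation system". Sections 3 and 8.3 place the baseline measurements before the 8-week intervention. Predicted-responder status comes from the screening stool sample and is not randomised.

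Sections 10.2 and 10.3 send the other endpoints through the same analysis. Those that are continuous and have a week-0 measurement under section 8.1.2 include calprotectin, GSRS, stool frequency, SCFAs and SIBDQ.

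**The concern.** Within a stratum, randomisation makes the expected prebiotics and placebo means at week 0 equal. A model that estimates a week-0 treatment difference spends data on a quantity known to be zero. What follows depends on the contrast reported:

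- **Change from week 0.** Any chance week-0 gap is subtracted in full, whereas with equal SDs only the fraction ρ of it predicts the later difference.
- **Difference at week 8.** The week-0 values then contribute nothing to the estimate, although they carry information about week 8.

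Either way the standard error is larger than the same data require, or at best equal to it. Section 4.4 plans on about 11 evaluable subjects per arm, so the loss deserves attention, and the same model is carried to several other endpoints.

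**Working it through.** **Inputs.** From the protocol: the model terms and visits (10.2), randomised treatment (8.2), 15 subjects per arm (4.4), entry scores of 3 to 5 (4.2), and an SD of 0.5 for mild UC (4.4). Assumed, because the protocol does not give them: ρ, the correlation between week 0 and week 8, from 0.2 to 0.7; and k, the week-0 SD divided by the week-8 SD. Data are taken as complete.

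**The protocol's own figure.** Section 4.4 states that "at least 11 subjects per group are needed for the primary outcome P-SCCAI", for means of 3.5 and 2.8, SD 0.5, two-sided 5% and 90% power. The normal approximation gives n = 2 × (1.960 + 1.282)² × 0.5² / 0.7² = 10.7, so 11: reproduced. The 0.7 is the planned difference between predicted responders and predicted non-responders, both on prebiotics. It is not a prebiotics-placebo difference, so it is not used below.

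**Are the week-0 means free?** In standard R formula coding (section 10 names R), the three main effects plus the three-way term have rank 20. This equals the 2 × 2 × 5 cells of treatment, status and visit, so every cell mean is free, including prebiotics and placebo at week 0 in each stratum.

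**Variance of the week-8 treatment effect in one stratum**, in units of 2σ²/n, with σ the week-8 SD and n the number per arm:

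- Before-after contrast, free week-0 means: 1 + k² − 2ρk, which is 2(1 − ρ) when k = 1.
- Plain week-8 contrast, free week-0 means: 1.
- Common week-0 mean for the two treatments: 1 − ρ².

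**Information lost** is 1 minus the constrained variance divided by the free variance:

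- Before-after: (k − ρ)² / (1 + k² − 2ρk), which is (1 − ρ)/2 when k = 1.
- Plain week 8: ρ².

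With equal SDs (k = 1):

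| ρ | Before-after variance | Constrained variance | Loss, before-after | Loss, plain week 8 |
|---|---|---|---|---|
| 0.2 | 1.60 | 0.96 | 40% | 4% |
| 0.3 | 1.40 | 0.91 | 35% | 9% |
| 0.5 | 1.00 | 0.75 | 25% | 25% |
| 0.7 | 0.60 | 0.51 | 15% | 49% |

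A generalised least squares calculation with five visits, a random intercept and 15 per arm agrees. In units of σ², the variances at ρ = 0.2 are 0.2133 free and 0.1280 constrained, a loss of 40%; at ρ = 0.7 they are 0.0800 and 0.0680, a loss of 15%.

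With unequal SDs, before-after loss for ρ from 0.2 to 0.7:

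| k | Range of loss |
|---|---|
| 0.5 | 0–9% |
| 0.75 | 0.5–24% |
| 1 | 15–40% |
| 1.5 | 56–64% |

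**Size of a chance gap**, with SD 0.5 at both visits and 15 per arm: the 95% range is ±1.96 × 0.5 × √(2/15) = ±0.36 points. The part wrongly carried into the before-after effect is (1 − ρ) × 0.36, about 0.29 at ρ = 0.2 and 0.11 at ρ = 0.7.

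**The case against.** **The model is standard and valid.** This stands. Under randomisation the contrast is unbiased with free week-0 means, so the issue is precision and exposure to chance imbalance.

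**The reported contrast is not named.** Section 10.2 lists model terms; its phrase about before and after intake can mean change from week 0 or the treatment difference at each visit. This stands, and both readings are therefore sized. On the second, no baseline gap is subtracted, and at low ρ the loss is small (4% at 0.2, 9% at 0.3).

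**The 15–40% rests on outside assumptions.** This also stands. Entry at scores 3 to 5 may lower ρ, but it may also shrink the week-0 SD relative to week 8, which pulls the before-after loss down. That restriction applies to P-SCCAI; calprotectin, SCFAs, GSRS and SIBDQ have no such entry limit.

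**It belongs in the SAP.** Only in part. Naming the contrast could wait for the SAP, but section 10.2 itself fixes week 0 as an outcome visit with a treatment term.

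**Stronger readings a reader might infer.** One is a power loss computed from 0.7 points, SD 0.5 and 11 per arm, or a comparison of the chance week-0 gap with 0.7. The protocol does not support this: section 4.4 plans 0.7 for a non-randomised comparison that the remedy leaves unconstrained, and it gives no prebiotics-placebo effect. Another is that the trial could miss a prebiotic effect because of this model. Section 10.1 does not use the model, and section 10.2 also plans direct between-group comparisons at each visit.

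**Conclusion.** The point holds as a loss of precision in a secondary model. Section 10.2 leaves the week-0 means of prebiotics and placebo free within each stratum, where randomisation makes a common mean valid. With known variances, the constrained estimator is never less precise than either contrast from the free model.

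The size cannot be fixed from the protocol, which gives neither ρ nor a separate week-8 SD. For a before-after difference with ρ from 0.7 to 0.2, the loss is 15–40% with equal SDs, 0.5–24% with a baseline SD three quarters of the week-8 SD, and about 0–9% with one half. For the plain week-8 difference it is 4–49% as ρ goes from 0.2 to 0.7. The figures assume complete data. There is no bias, and the primary tests in 10.1 are not affected.

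**What to change.** In section 10.2, keep week 0 among the outcomes but give prebiotics and placebo one common week-0 mean within each stratum, with treatment terms only at post-baseline visits. Alternatively, use the week-0 value as a covariate and only post-baseline visits as outcomes. In addition:

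- Leave week 0 free to differ between predicted responders and predicted non-responders, since that factor is not randomised.
- Let variances differ by visit. A random intercept alone implies equal variances, which the 3-to-5 entry range makes doubtful for P-SCCAI.
- Report the week-8 prebiotics-placebo difference in each stratum, and its difference between strata, from this model.
- Apply the same to calprotectin, GSRS, stool frequency, SCFAs and SIBDQ.

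The cost is a few sentences in section 10.2 or the SAP and a small change to the model code. No further data or subjects are needed.
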